### 5.2 Physical Examination

The physical examination is considered standard of care prior to surgery.

### 5.3 Diagnostic Tests, Scales, Measures, etc.

This study will involve a quantitative assessment of prospectively collected computed tomography, radiographic, and patient reported outcomes data. Function measures include Range of Motion (ROM) scores. Outcomes measures include the HOOS, PROMIS 10, and HAS evaluation (cup placement measurements conducted on specific MAKO software).

### 5.4 Safety Evaluation

Subject safety will be monitored by adverse events, physical examinations, and questionnaires.

## 6 STATISTICAL CONSIDERATIONS

### 6.1 Sample Size and Power

Patient characteristics and demographics will be analyzed using Chi-square or Fisher's exact test as appropriate for categorical variables and parametric and non-parametric hypotheses tests for continuous variables as appropriate. The central hypothesis will be evaluated using a univariate logistic regression model to determine the accuracy of cup placement using the NON-ROBOTIC ARM group as the reference. Confounding factors will be controlled for in the model and interaction between terms will also be evaluated.

Data will be analyzed by the West Virginia University biostatistics team/core; other tests may be added at the discretion of those experts.

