## **2.2 Secondary Objectives (or Aim)**

**Specific Aim #1:** Determine the accuracy of placement of robotic-arm assisted acetabular cups versus manual cup placement. The working hypothesis is that robotic-arm assisted cup placement will demonstrate more accurate cup placement compared to conventional manual cup placement.

**Specific Aim #2:** Assess the frequency with which the robotic-arm assisted placements of acetabular cups are accurately placed compared to the surgical plan. The working hypothesis is that robotic-arm assisted THA will demonstrate greater accuracy by adhering to the surgical plan more frequently than non-robotic-arm assisted cases.

**Specific Aim #3:** Examine the patient reported outcomes of robotic-arm assisted THA subjects. The working hypothesis is that subjects undergoing robotic-arm assisted acetabular cup placement will report better outcomes than subjects with conventional manual cup placements.

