### **3.4 Total Number of Study Sites/Total Number of Subjects Projected**

To achieve accuracy of cup placement within 5 degrees of the target version (40 degrees  $\pm 5$ ) and abduction (20 degrees  $\pm 5$ ) angles 90 percent of the time, we will enroll 24 subjects per provider. The study will be conducted at two investigative sites in the United States and recruitment will stop when a total of 192 subjects are enrolled at these facilities. It is expected that 120 subjects will be enrolled at WVU Medicine, 48 subjects will be enrolled at Allegheny General Hospital (AGH), and 24 subjects at Forbes Regional Hospital.

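### No analysis of cup accuracy in degrees is planned: the only model named needs a yes/no outcome, and its cut-off is unsettled

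*Combined protocol and SAP*

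**What the plan says.** Section 6.1 names one model for the central hypothesis: "The central hypothesis will be evaluated using a univariate logistic regression model to determine the accuracy of cup placement", with the non-robotic group as the reference. The tests for continuous variables in the same section are attached to patient characteristics and demographics, not to cup angles. A closing sentence lets the biostatistics team add further tests but names none.

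Section 2.2 lists two questions about the cup. Aim 1 is to "Determine the accuracy of placement of robotic-arm assisted acetabular cups versus manual cup placement", with no scale given. Aim 2 is to "Assess the frequency with which the robotic-arm assisted placements of acetabular cups are accurately placed compared to the surgical plan".

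Section 5.3 describes the measurement: "This study will involve a quantitative assessment of prospectively collected computed tomography, radiographic, and patient reported outcomes data". Section 2.1 says that CT and HAS were chosen to describe cup placement fully.

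The yes/no outcome is never defined outright. The nearest statement is in Section 3.4, "To achieve accuracy of cup placement within 5 degrees of the target version" (and likewise for abduction), with "angles 90 percent of the time, we will enroll 24 subjects per provider".

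**The concern.** The study pays for CT and HAS measurement of every hip, and the one prespecified model then needs each hip reduced to in or out. A cup 5.1 degrees off target counts the same as one 20 degrees off, and a cup on target counts the same as one 4.9 degrees off. Three things are at stake.

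- **Interpretation.** The report could not say, with a confidence interval, how many degrees closer robotic cups come to target.
- **Dependence on the cut-off.** The yes/no result turns on a range that the document states in two ways.
- **Power.** If the manual arm already does fairly well, a real gain in precision could be missed with 192 subjects, although the measured angles might show it.

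**Working it through.** **Inputs from the document.** 8 surgeons and 24 subjects each (Section 3.1); within 5 degrees, 90 percent of the time (Section 3.4).

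**Inputs assumed.** 1:1 allocation (96 per arm), two-sided 5%, no dropout, robotic success rate 90%, manual rate 70% to 80%, independent normal errors centred on target with equal SD on the two angles. Success means both angles within 5 degrees. The 90% in Section 3.4 is not tied to an arm. No control rate, SD, alpha, power or allocation ratio is given.

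**1. The plan's own figures.** 8 × 24 = 192 and 120 + 48 + 24 = 192, so the total agrees. The basis for 24 per surgeon cannot be reproduced from what is stated.

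**2. The cut-offs side by side.**

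| | Abduction | Version |
|---|---|---|
| Section 1.1 | 40 ± 10 | 20 ± 5 |
| Section 3.4 | 20 ± 5 | 40 ± 5 |

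The widths differ for abduction, and the angle labels are exchanged.

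**3. From success rate to SD.** With p = [2Φ(5/σ) − 1]², σ = 5 / Φ⁻¹((1 + √p)/2). This gives σ = 2.566 at 90%, 3.336 at 75% and 3.089 at 80%.

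**4. Yes/no power, 75% v 90%.** The pooled rate is 0.825. SE under the null = √(2 × 0.825 × 0.175/96) = 0.0548. SE under the alternative = √((0.1875 + 0.09)/96) = 0.0538. Power = Φ((0.15 − 1.96 × 0.0548)/0.0538) = 0.79. Simulating the likelihood-ratio test of the logistic model gives about 80%.

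**5. Larger of the two absolute deviations, 75% v 90%.** For two independent normal errors, the larger absolute error has mean 2σ/√π = 1.128σ and variance (1 − 2/π)σ² = 0.363σ². The difference in means is 1.128 × (3.336 − 2.566) = 0.87 degrees. SE = √(0.363 × (3.336² + 2.566²)/96) = 0.259. Power = Φ(0.87/0.259 − 1.96) = 0.92, and simulation agrees. The 95% interval would be about ± 1.96 × 0.259 = 0.51 degrees.

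**6. Across manual rates (robotic 90%; simulated, rounded).**

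| Manual rate | Logistic, in/out | t-test, larger deviation |
|---|---|---|
| 70% | about 95% | about 99% |
| 75% | about 80% | about 92% |
| 78% | about 64% | about 80% |
| 80% | about 50% | about 66% |

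**7. One angle alone, 75% v 90%.** The absolute error of one angle has mean 0.798σ and the same variance, 0.363σ². The difference is 0.798 × 0.770 = 0.61 degrees with SE 0.259, so power = Φ(0.61/0.259 − 1.96) = 0.66. That is below the yes/no analysis.

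**8. Gross outliers.** Suppose manual errors match robotic errors except in about 20% of hips, where the SD is 10 degrees; about 75% of manual hips are then in range. Power on the larger deviation is about 54% for a rank test and 97% for a t-test, against 80% for the yes/no analysis.

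**9. Effect of the cut-off.** Take the errors of step 5 and apply the Section 1.1 widths (one angle ± 10, the other ± 5). Manual success becomes 0.997 × 0.866 = 0.86, and robotic success becomes 1.000 × 0.949 = 0.95. Simulated logistic power falls from about 80% to about 55%. An analysis in degrees does not change with the width, though it still needs an agreed target.

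**The case against.** A yes/no endpoint is defensible here. Section 1.1 frames the risk of dislocation as a matter of falling outside a range, and Section 3.4 speaks of accuracy as within 5 degrees. Aim 1 gives no scale. Its visible difference from Aim 2 is the comparator, manual placement as against the surgical plan, so reading Aim 1 as a question about degrees is an inference. Section 6.1 also ties the logistic model to the central hypothesis rather than to each aim, and it allows further tests. All of this stands, and it is why the logistic analysis should stay. It does not supply a degree-scale analysis: permission to add unnamed tests is not prespecification.

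A reader might go further and infer that the yes/no analysis necessarily wastes power, or that any analysis in degrees would do better. The documents do not support that. They give no control rate or SD, so every power figure is a scenario. At a manual rate of 70% the logistic model already has about 95% power. With normal errors, a single-angle analysis does worse than the joint yes/no outcome (66% v about 80%). Nor is a rank test a safe lower bound: it loses to the yes/no analysis when the manual arm differs mainly by a few badly placed cups, which is close to the malpositioning that Section 1.1 describes.

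**Conclusion.** The point holds in a limited form. The plan prespecifies no accuracy effect in degrees, although the angles are measured, and its one named model rests on an outcome whose range is stated inconsistently. Both follow from the text alone.

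The power loss is conditional. Under the stated assumptions, the logistic model falls short of a t-test on the larger deviation by about 4 points at a manual rate of 70%, 12 at 75%, and 16 at 78% and at 80%. It would be wrong to conclude that the trial is underpowered or that the binary endpoint is an error. The change is worth making because it is cheap and gives Aim 1 an interpretable result.

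**What to change.** - Reconcile the target angles, their labels and the ranges between Sections 1.1 and 3.4, and define the in-range outcome explicitly.
- Keep the logistic in-range analysis for the frequency question.
- In Section 6, name one lead continuous measure for Aim 1: the larger of the two absolute deviations from target, in degrees. Analyse it in a linear model with arm and surgeon, and report the mean difference with a 95% confidence interval. Use robust or bootstrap standard errors because deviations are skewed.
- Report abduction and version deviations separately as descriptive results, and use a rank test as a sensitivity analysis only.
- State where this result stands in the hierarchy relative to the logistic one.

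The cost is a paragraph in Section 6 and one more model on data already being collected, with no extra subjects, scans or visits. The drawbacks are the robustness check for skew and a second accuracy result, which may not agree with the first.

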## 7 SAFETY MANAGEMENT

The PI and Co-Is will be responsible for the safety management of this study. Since the study procedures are not greater than minimal risk, serious adverse events (SAEs) are not expected. If any unanticipated problems related to the research involving risks to subjects or others happen during the course of this study (including SAEs), they will be reported to the IRB. AEs that are not serious but that are notable and could involve risks to subjects will be summarized in narrative or other format and submitted to the IRB at the time of continuing review.

## **7.1 Clinical Adverse Events**

Clinical adverse events (AEs) will be monitored throughout the study.

## **7.2 Adverse Event Reporting**

Unanticipated problems related to the research involving risks to subjects or others that occur during the course of this study (including SAEs) will be reported to the IRB in accordance with WVU IRB SOP: Unanticipated Problems Involving Risks to Subjects. AEs that are not serious but that are notable and could involve risks to subjects will be summarized in narrative or other format and submitted to the IRB at the time of continuing review.

## **7.3 Definition of an Adverse Event**

An adverse event is any untoward medical occurrence in a subject who has received an intervention (drug, biologic, or other intervention). The occurrence does not necessarily have to have a causal relationship with the treatment. An AE can therefore be any unfavorable or unintended sign (including an abnormal laboratory finding, for example), symptom, or disease temporarily associated with the intervention, whether or not considered related to the intervention.

All AEs (including serious AEs) will be noted in the study records and on the CRF with a full description including the nature, date and time of onset, determination of non-serious versus serious, intensity (mild, moderate, severe), duration, causality, and outcome of the event.

## **7.4 Definition of a Serious Adverse Event (SAE)**

An SAE is any adverse experience that results in any of the following outcomes:

- Death;
- Life-threatening event (at risk of death at the time of the event);
- Inpatient hospitalization or prolongation of existing hospitalization required;
- Persistent or significant disability/incapacity; and
- Congenital anomaly/birth defect in the offspring of a subject.

Important medical events that may not result in death, be life-threatening, or require hospitalization may be considered a serious adverse event when, based upon appropriate medical judgment, they may jeopardize the subject and may require medical or surgical intervention to prevent one of the outcomes listed in this definition.

A distinction should be drawn between serious and severe AEs. A severe AE is a major event of its type. A severe AE does not necessarily need to be considered serious. For example, nausea which persists for several hours may be considered severe nausea, but would not be an SAE. On the other hand, a stroke that results in only a limited degree of disability may be considered a mild stroke, but would be an SAE.

## **7.5 Relationship of SAE to study drug or other intervention**

The relationship of each SAE to the study intervention should be characterized using one of the following terms in accordance with WVU IRB Guidelines: definitely, probably, possibly, unlikely, or unrelated.

## **7.6 IRB Notification of SAEs and Other Unanticipated Problems**

The Investigator will promptly notify the IRB of all on-site unanticipated, serious Adverse Events that are related to the research activity. Other unanticipated problems related to the research involving risk to subjects or others will also be reported promptly. Written reports will be filed using the IRB system and in accordance with the timeline in the IRB SOP. External SAEs that are both unexpected and related to the study intervention will be reported promptly after the investigator receives the report.

## **7.7 Follow-up report**

If an SAE has not resolved at the time of the initial report and new information arises that changes the investigator's assessment of the event, a follow-up report including all relevant new or reassessed information (e.g., concomitant medication, medical history) should be submitted to the IRB. The investigator is responsible for ensuring that all SAEs are followed until either resolved or stable.

# **8 STUDY ADMINISTRATION**

## **8.1 Treatment Assignment Methods**

The method of THA surgery (robotic-arm assisted or not) will be randomly assigned using a pre-populated randomization schedule after patient consent. Patients in the control group will undergo traditional THA surgery without robotic-arm assistance. The same variables will be collected for both study groups

## **8.2 Data Collection and Management**

### **1. Confidentiality**

- A master list containing personal health information (PHI) and subject identification (ID) number separate from data forms (paper and electronic) that have only a study ID number. The master list will be kept on a separate computer, removable disk drive, or in a locked file cabinet.
- Data files will be stored electronically on a WVU password protected restricted drive. Only the key study personnel associated with this study will have access to the data files.

### **2. Security**

The subject master list will be stored electronically on a password protected Excel spreadsheet housed on secure servers at West Virginia University. Patient binders and information will be stored in a locked cabinet in the clinical research coordinator's locked office.

### 3. Destruction

All data will be retained for 10 years and be kept in a locked room. Each document will be marked with a destroy date with earliest dates at the front.

## **8.3 Confidentiality**

All data and records generated during this study will be kept confidential in accordance with Institutional policies and The Health Insurance Portability and Accountability Act (HIPAA) on subject privacy. The Investigator and other site personnel will not use such data and records for any purpose other than conducting the study.

The Institution owns all Study Data, excluding Site's patient medical records and Investigator's personal notes. Institution hereby grants to the Site a non-exclusive, non-transferable, non- sub-licensable right to use the Study Data solely for its own internal, non-commercial research and educational purposes.

In performance of this Study, Site shall not provide to Institution any individually identifiable health information. All Study Data provided by Site to Institution shall be de-identified. Any individually identifiable health information collected or produced by Site or Site Investigator shall be in accordance with the Protocol and only for the purpose of complying with applicable law, provided that all such uses are disclosed in the IRB-approved ICF. Institution may use information that is not identifiable under any applicable U.S. laws for any research and development purpose. Institution will not contact any Study subjects, unless permitted by the ICF.

## **8.4 Regulatory and Ethical Considerations**

IRB approval will be obtained from the West Virginia University IRB board. The study will be conducted according to the IRB/West Virginia University policies and procedures. This study will be reviewed by the IRB on a yearly basis.

The proposed study anticipates recruiting a proportion of racial/ethnic minorities (African Americans, Asian-Americans, and Hispanics) as well as non-Hispanic and white subjects. The study will not include children or prisoners.

It is the Investigators' responsibility to conduct the protocol under the current version of Declaration of Helsinki, ICH Guidelines, Good Clinical Practice, and the rules of the West Virginia University IRB. The investigator must ensure that the patient's anonymity be maintained within the data.

All paper records will be kept in locked file cabinets in a locked office. All electronic records of study data will be stored on password protected computers in restricted drives. Clinical information will not be released without written permission of the patient, except as necessary for monitoring by the IRB. Consent procedures and forms, and the communication, transmission, and storage of patient data will comply with individual site IRB and requirements for compliance with HIPAA.

**Study Discontinuation:** Participants will be informed that they may discontinue the study at any time, for any reason. They will be assured that the medical care which they receive at the participating facility will not be affected should they elect to discontinue participation in the study.

## **8.5 Data and Safety Monitoring Plan**

The PI and Co-Is will be responsible for safety management of this study. The study progress will be monitored quarterly with the study team. Since the study procedures are not greater than minimal risk, SAEs are not expected. If any unanticipated problems related to the research involving risks to subjects or others happen during the course of this study (including SAEs), these will be reported to the IRB in accordance with IRB SOP: Unanticipated Problems Involving Risks to Subjects. Adverse Events that are not serious but that are notable and could involve risks to subjects will be summarized in narrative or other format and submitted to the IRB at the time of continuing review.

## **8.6 Risk Assessment**

As a hip replacement candidate, all risks for this surgical procedure will be explained in detail to you by your surgeon prior to surgery. Some, but not all, of the risks involved with surgery are blood clots, infection, fracture, dislocation, change in leg length, and prosthesis/implant loosening.

This study requires you to undergo two CT scans of your pelvis. Exposure to radiation is associated with an increased risk of cancer. Patients will be exposed to additional radiation from the CT scan 1-2 times over the course of the study based on which TREATMENT METHOD [arm] they are randomized to. The risk of developing cancer as a result of

exposure to radiation depends on the part of the body exposed, the individual's age at exposure, and the individual's gender. For the purpose of radiation protection, a conservative approach that is generally used is to assume that the risk for adverse health effects from cancer is proportional to the amount of radiation dose absorbed and that there is no amount of radiation that is completely without risk. The possibility of fatal cancer from radiation is approximately 1 chance in 2000 for an equivalent radiation dose of 10 milliSievert. The equivalent radiation dose range for one CT scan of the hip is 0.2-25 milliSievert, depending on patient size. Therefore, the possibility of fatal cancer from radiation is approximately 1 chance in 2000, equal to the dose from one or two hip CT scans, depending upon patient height and weight.

This study may involve risks to the unborn child. For this reason, women who are pregnant will not be accepted. If you are a woman who could become pregnant, you will not be allowed to participate in the study until you have a negative pregnancy test. You must use a medically approved method of birth control while you are on this study.

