## 4 STUDY PROCEDURES

	Screening/Pre-Op (-30 days)	Visit 2/Intra-op	Visit 3/3-6 months (± 1 months)	Visit 4/1 year (+ 3 months)	Visit 5/2 year (+ 6 months)
Consent	X				
Inclusion/Exclusion	X				
Demographics	X				
Medical History	X				
Surgical Details		X			
Function Evaluation/ROM	X		X	X	
HOOS	X		X	X	X
PROMIS 10	X		X	X	X
Dislocation/Ad Events			X	X	X
Radiographs	X		X	X	X
Computed Tomography	X		X		
HAS Analysis			X	X	X
Con Meds	X	X	X	X	X
Physical Exam	X				

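### Section 8.6 gives one fatal-cancer risk of about 1 in 2000 for one or two CT scans, but its own inputs give up to 1 in 800 for one scan and 1 in 400 for two if 25 mSv per scan is reached

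*Combined protocol and SAP*

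**What the plan says.** Section 8.6 (Risk Assessment) builds its radiation statement from three inputs.

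- A risk coefficient: "The possibility of fatal cancer from radiation is approximately 1 chance in 2000 for an equivalent radiation dose of 10 milliSievert".
- A dose-response rule, described there as a conservative convention, which is to "assume that the risk for adverse health effects from cancer is proportional to the amount of radiation dose absorbed".
- A dose range: "The equivalent radiation dose range for one CT scan of the hip is 0.2-25 milliSievert, depending on patient size".

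From these it infers, with the word 'Therefore', a single fatal-cancer risk: "radiation is approximately 1 chance in 2000, equal to the dose from one or two hip CT scans, depending upon patient height and weight".

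On the number of scans, the same section says "This study requires you to undergo two CT scans of your pelvis", and also "Patients will be exposed to additional radiation from the CT scan 1-2 times over the course of the study", according to the randomised arm. The "Computed Tomography" row of the Section 4 schedule marks two time points, read as screening/pre-op and 3-6 months, with no split by arm.

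**The concern.** The concluding sentence attaches one risk to one scan and to two scans alike, although the dose per scan is said to vary 125-fold (25/0.2) and the risk is said to scale with dose. The qualifier about height and weight admits that dose varies but leaves the risk fixed. Under the section's own rule both cannot hold.

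This is the only fatal-risk figure the document gives for a study procedure. No other passage corrects it: the discussion in Section 8.7 names surgical and privacy risks but not radiation. Sections 7 and 8.5 describe the study procedures as no more than minimal risk. That description is not disputed here; the point is only that the number beside it should follow from its inputs. Section 8.6 addresses the reader as a subject, so the sentence may also appear in subject-facing text. The consent pages are not in the reviewed text, so whether subjects saw it cannot be judged.

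**Working it through.** **Inputs, all from Section 8.6.** Risk 1/2000 at 10 mSv; risk proportional to dose; 0.2 to 25 mSv per scan; one or two scans.

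**Formula.** Risk = (total mSv / 10) × (1/2000) = total mSv / 20,000. Two scans are made on the same subject, so the same per-scan dose D is used for each. One scan gives 1 in 20,000/D; two scans give 1 in 10,000/D.

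**Reproducing the plan's figure.** Setting total mSv / 20,000 = 1/2000 gives a total of 10 mSv. The stated value is therefore recovered with one scan at 10 mSv or two scans at 5 mSv each, and at no other dose.

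**Across the stated range.** The last row uses the section's stated maximum. The 15 and 20 mSv rows are assumed lower maxima, shown because the documents do not say what dose eligible subjects reach.

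| D, mSv per scan | One scan | Ratio to 1/2000 | Two scans | Ratio to 1/2000 |
|---|---|---|---|---|
| 0.2 | 1 in 100,000 (0.001%) | 0.02 | 1 in 50,000 (0.002%) | 0.04 |
| 5 | 1 in 4000 | 0.5 | 1 in 2000 (0.05%) | 1 |
| 10 | 1 in 2000 (0.05%) | 1 | 1 in 1000 | 2 |
| 15 | 1 in 1333 | 1.5 | 1 in 667 | 3 |
| 20 | 1 in 1000 | 2 | 1 in 500 | 4 |
| 25 | 1 in 800 (0.125%) | 2.5 | 1 in 400 (0.25%) | 5 |

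**Where the stated value stops covering everyone.** It is exceeded once D is above 10 mSv for one scan or above 5 mSv for two. These thresholds are 10/25 = 40% and 5/25 = 20% of the stated maximum.

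**The case against.** The best defence reads the sentence as an equivalence: 10 mSv is what one scan delivers in a larger patient, or two scans deliver in a smaller one. Both 10 and 5 mSv lie inside the stated range, and the wording is approximate. On that reading no arithmetic step is false, and the fault is an undisclosed range.

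This does not rescue the sentence. Body size does not set the number of scans. Section 8.6 requires two, the Section 4 schedule shows two, and any difference in additional exposure is tied to the arm. A larger patient who receives 10 mSv from one scan receives 20 mSv from two, which by the section's own rule is 1 in 1000. The stated figure is then half the implied risk, without any appeal to the 25 mSv extreme.

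Several parts of the objection do stand:

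- The sentence does not present 1 in 2000 as a maximum, and it overstates the risk for any total below 10 mSv, by 50-fold for one scan at 0.2 mSv. That is the cautious direction.
- The 1 in 400 figure needs the maximum dose twice in one eligible subject. Section 3.7 excludes BMI above 40 and dose is said to depend on patient size, so the documents do not show that this happens.
- The dose range is for the hip, while the study scans are of the pelvis. The section itself says that cancer risk from "exposure to radiation depends on the part of the body exposed", and it gives no dose specific to the pelvis.
- The fault could lie in the dose range and not in the conclusion. The documents cannot settle which.
- The two statements on scan numbers can be read together as total scans versus scans beyond usual care. That is a point of clarity and adds no weight to the finding.

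**Conclusion.** The concern holds. The inference in Section 8.6 does not follow from its inputs, except at a total dose of 10 mSv. Taking those inputs as written, the risk runs from about 1 in 100,000 to 1 in 800 for one scan and from 1 in 50,000 to 1 in 400 for two. The printed 0.05% compares with 0.125% and 0.25% at the upper ends, an understatement of 2.5-fold and 5-fold.

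Those multiples rest on the section's coefficient, on proportionality, and on 25 mSv being reached in eligible subjects. If the true maximum is lower they shrink, as the table shows, but 1 in 2000 covers every subject only if no scan exceeds 10 mSv (one scan) or 5 mSv (two scans). The matter should be corrected. It is an error in a risk statement and has no bearing on sample size, endpoints or analysis.

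**What to change.** 1. Confirm that the stated hip-CT dose range applies to the pelvic scans the study uses and to the eligible population.
2. Replace the concluding sentence with the range that follows. On the present figures: one scan, 0.2 to 25 mSv, about 1 in 100,000 to 1 in 800; two scans, 0.4 to 50 mSv, about 1 in 50,000 to 1 in 400. If 1 in 2000 is kept as an illustration, label it as the risk at a total of 10 mSv.
3. In the same edit, state which scans are additional to usual care in each arm, so that the two statements in Section 8.6 and the Section 4 schedule can be read together and the reader can see which range applies.
4. Carry the change into any subject-facing text that uses the same sentence.

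The cost is one check, one replaced sentence and one clarifying statement. On the present inputs, the disclosed risk becomes less favourable at its upper end. Nothing in the imaging schedule, design or analysis needs to change.
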